### 6.3.1.7 Additional follow-up for ILD/pneumonitis

**Table 6-6 LEE011 dose adjustment and management recommendation for ILD/pneumonitis (CTCAE v 4.03)**

Grade	Dose Adjustment and Management Recommendations
1 (asymptomatic)	No dose adjustment required. Initiate appropriate medical therapy and monitor as clinically indicated.
2 (symptomatic)	Interrupt LEE011 dose until recovery to Grade ≤1, then resume LEE011 at the next lower dose level*.
3 and 4 (severe)	Discontinue LEE011

\* An individualized benefit-risk assessment should be performed before resuming LEE011

### 6.3.1.8 Guidance for all other adverse reactions

Consider performing an analysis of serum potassium, calcium, phosphorus, and magnesium for all adverse reactions, if indicated. If electrolyte values are outside of the normal range, interrupt LEE011/placebo administration, correct electrolytes with supplements or appropriate therapy as soon as possible, and repeat electrolyte testing until documented normalization of the electrolytes.

For all other adverse events, including Toxic Epidermal Necrolysis (TEN), which is a grade 4 event by CTCAE, please follow recommendations in [Table 6-7](#).

**Table 6-7 LEE011/placebo dose adjustment and management recommendation for all other adverse reactions (CTC AE v4.03)**

Grade	Dose Adjustment and Management Recommendations
1	No dose adjustment required. Initiate appropriate medical therapy and monitor.
2	Dose interruption until recovery to grade $\leq 1$ . Initiate appropriate medical therapy and monitor. Re-initiate LEE011/placebo at the same dose. 
 
• If the same toxicity recurs at grade 2, interrupt LEE011/placebo until recovery to grade <math>\leq 1</math>. Re-initiate LEE011/placebo at the next lower dose level.
 

3	Dose interruption until recovery to grade $\leq 1$ . Initiate appropriate medical therapy and monitor. Re-initiate LEE011/placebo at the next lower dose level. 
 
• If toxicity recurs at grade 2: temporary dose interruption until recovery to grade <math>\leq 1</math> and reduce LEE011/placebo dose the next lower dose level.
 
• If toxicity recurs at grade 3, discontinue LEE011/placebo.
 

4	Discontinue LEE011/placebo and treat with appropriate medical therapy.

#### 6.3.1.8.1 Adjustment of starting dose in special populations

##### Renal impairment

Insufficient data are available to provide a dosage recommendation for LEE011 in patients with renal impairment. A study in non-cancer patients with varying degrees of renal impairment and matched subjects with normal renal function is ongoing [CLEE011A2116]. Refer to [ribociclib Investigators Brochure] for more details. Based on rat ADME data, LEE011 was predominantly excreted in the bile as metabolites, with limited excretion of unchanged drug in urine.

Increases in tamoxifen serum concentrations did not occur in a 51 year-old woman with renal impairment who received tamoxifen for metastatic breast cancer, however further studies are lacking (Sutherland 1984).

Studies with goserelin in female patients with renal impairment do not indicate a need for dose adjustment with the use of the depot formulation (Zoladex® Prescribing Information AstraZeneca).

Renal impairment does not affect letrozole or anastrozole PK in humans (Femara® Prescribing Information Novartis, Arimidex® Prescribing Information AstraZeneca).

Patients with baseline renal impairment or with AST/ALT or bilirubin values beyond certain thresholds as specified in the eligibility criteria are excluded from the study. Patients who experience renal impairment of grade 2 or higher during the treatment period should discontinue treatment and should be followed for safety assessments.

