#### 1.2.1.1.2 Safety pharmacology and toxicology

*In vivo* cardiac safety studies demonstrated a signal for QT prolongation with the potential to induce incidences of premature ventricular contractions (PVCs) at higher exposure levels.

The effects of LEE011 on the bone marrow (hypocellularity), lymphoid system (lymphoid depletion), intestinal mucosa (atrophy), skin (atrophy), bone (decreased bone formation) and testes (atrophy) are considered to be related to the pharmacological inhibition of cell replication in these tissues due to CDK4/6 inhibition.

[figure not shown]
An increased number of ovarian corpora lutea was observed in a single female dog in the 4-week toxicity study at the highest dose tested (20 mg/kg/day) and this effect could also be related to the pharmacology of LEE011 (arrest of estrous cycle).

The liver, bile system and gall bladder (proliferative changes, cholestasis, sand-like gallbladder calculi and inspissated bile) and the kidney (concurrent degeneration and regeneration of tubular epithelial cells) were identified as additional target organs of toxicity which are not likely related to the primary pharmacology of LEE011.

Inflammatory changes in the lungs of dogs were considered secondary to aspiration of test article and are indicative of the irritant potential of the formulated test-article in the respiratory tract. Correlating hematological and/or biochemistry changes were seen for the effects described in the bone marrow, lymphoid system and liver.

Generally all changes demonstrated either reversibility or a clear tendency towards reversibility. In the rat, there was no evidence of teratogenicity however LEE011 was embryofetotoxic. Data from a rabbit embryofetal development study, shows that LEE011 is teratogenic in the rabbit in the absence of maternal toxicity.

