**Table 1-2 Serious adverse events with a suspected causal relationship with LEE011 single agent**

Serious suspected adverse events which have occurred with LEE011 (single agent)	
System Organ Class Preferred Term	Preferred Term
Blood and lymphatic system disorders	Anaemia, Febrile neutropenia, Neutropenia, Thrombocytopenia
Gastrointestinal disorders	Diarrhoea, Nausea, Pancreatitis
General disorders and administration site conditions	Generalized oedema
Infections and infestations	Herpes simplex
Investigations	Blood creatinine increased, Electrocardiogram QT prolonged

Refer to [LEE011 Investigators Brochure] for more details.

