## 6 Treatment

### 6.1 Study treatment

For this study, the term “investigational drug” refers to Novartis study drug LEE011. The other drugs to be used in this study are tamoxifen, letrozole, anastrozole, and goserelin. Study treatment in this study refers to the triple combination of the investigational drug, LEE011/placebo, and tamoxifen/NSAI and goserelin. Refer to [Section 4](#) for the criteria determining treatment with tamoxifen or NSAI.

Novartis will supply LEE011/placebo as 200 mg hard gelatin capsules as individual patient supply packaged in bottles. Tamoxifen, letrozole, anastrozole and goserelin will be procured locally as they are commercially available drugs in each participating country according to local practice and regulation. Storage conditions are described in the medication label. Tamoxifen, letrozole, anastrozole, and goserelin should be used in accordance with the locally approved label (SmPC). Medication labels will comply with the legal requirements of each country and be printed in the local language.

All dosages prescribed and dispensed to the patient and all dose changes during the study must be recorded on the Dosage Administration Record eCRF.

The study met its primary efficacy endpoint (PFS) at the time of the primary analysis. It also met the key secondary efficacy endpoint of OS at the time of the pre-planned 2nd interim OS analysis. Given the demonstrated survival benefit, patients and investigators will be unblinded to the treatment allocation. Additionally, patients who remain on study treatment and are currently allocated to the placebo combination arm, will be given the opportunity to cross over to the LEE011 combination arm.

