### 6.1.4 Guidelines for continuation of treatment

For guidelines for continuation of treatment, refer to [Section 6.3](#), Dose Modifications.

Patients who permanently discontinue any component of endocrine combination partner (tamoxifen/NSAI) for any reason must discontinue LEE011/placebo and goserelin and move to End of Treatment Phase, but will remain on study for efficacy and survival follow-up evaluations. Patients who permanently discontinue LEE011/placebo and/or goserelin for any

[REDACTED]

reason other than disease progression may continue on tamoxifen or a NSAID per investigator's discretion until disease progression, unacceptable toxicity, death or discontinuation from study treatment due to any other reason and continue to be followed for safety and/or efficacy.

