#### **7.1.5.1 Discontinuation of study treatment**

Patients **may** voluntarily discontinue from the study treatment for any reason at any time.

If a patient decides to discontinue from the study treatment, the investigator must make reasonable effort (e.g. telephone, e-mail, letter) to determine the primary reason for this decision and record this information in the patient's chart and on the appropriate CRF pages. They may be considered withdrawn if they state an intention to withdraw, fail to return for visits, or become lost to follow-up for any other reason.

The investigator should discontinue study treatment for a given patient if, he/she believes that continuation would be detrimental to the patient's well-being.

Patients may be withdrawn from the study treatment if any of the following occur:

- Adverse Event (including, but not limited to  $QTcF \geq 501$  msec, confirmed at repeated ECG measurements and recurrent after dose adjustment was performed; documented episode of ventricular tachycardia, or ventricular fibrillation)
- Lost to follow-up
- Physician decision
- Progressive Disease

- Protocol deviation
- Study terminated by sponsor
- Technical problems

Patients must be withdrawn from the study treatment if any of the following occur:

- Pregnancy
- Death
- Subject/Guardian decision

In addition to the general withdrawal criteria, the following study specific criteria will also require study treatment discontinuation:

- Adjustments to study treatment that result in discontinuation. Please refer to [Section 6.3](#).
- Use of prohibited medication. Please refer to [Section 6.4.3](#).

Patients who discontinue study treatment should NOT be considered withdrawn from the study. They should return for the assessments indicated in [Section 7.1](#). If they fail to return for these assessments for unknown reasons, reasonable effort (e.g. telephone, email, letter) should be made to contact them as specified in [Section 7.1.5](#).

Patients who discontinue study treatment should undergo an End of Treatment (EOT) visit followed by a 30 day safety follow-up.

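### Renal impairment on treatment: Section 6.3.1.8.1 says discontinue from grade 2, but Section 6.3.1.8 and Table 6-7 tell sites to restart LEE011 after a first grade 2 or grade 3 event

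*Protocol*

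**What the plan says.** The renal rule is the last sentence of Protocol Section 6.3.1.8.1, under a heading about starting dose in special populations: "Patients who experience renal impairment of grade 2 or higher during the treatment period should discontinue treatment". It adds that these patients are followed for safety.

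The parent section, 6.3.1.8, gives the general instruction: "For all other adverse events, including Toxic Epidermal Necrolysis (TEN), which is a grade 4 event by CTCAE, please follow recommendations in" Table 6-7. Neither that sentence nor the table mentions renal events. For grade 2, Table 6-7 says to interrupt until grade 1 or lower, and then: "Initiate appropriate medical therapy and monitor. Re-initiate LEE011/placebo at the same dose". A first grade 3 event is also interrupted and restarted, one dose level lower. Grade 4 stops LEE011/placebo.

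Two other places bear on which text prevails. Section 6.3.1.4 leaves management to clinical judgment, but makes stopping mandatory where Tables 6-3 to 6-7 require it or where Section 7.1.5.1 lists the event. Section 7.1.5.1 includes among its mandatory criteria "Adjustments to study treatment that result in discontinuation", with a reference to Section 6.3.

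On what is to be stopped, Section 6.1 says: "Study treatment in this study refers to the triple combination of the investigational drug, LEE011/placebo, and tamoxifen/NSAI and goserelin". Section 6.1.4 says that a patient who permanently stops LEE011/placebo and/or goserelin for a reason other than progression "may continue on tamoxifen or a NSAID per investigator's discretion until disease progression".

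**The concern.** The same patient with the same event receives opposite instructions. A site that opens the dose-modification table restarts LEE011; a site that reads on to the end of the next subsection takes the patient off it. At stake is renewed exposure in someone whom the protocol's own renal rule would have stopped.

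The event is foreseeable. Section 1.2.1.1.2 reports that, alongside the liver and biliary system, "the kidney (concurrent degeneration and regeneration of tubular epithelial cells) were identified as additional target organs of toxicity". Table 1-2 lists, among serious events suspected to be related to single-agent LEE011, "Blood creatinine increased, Electrocardiogram QT prolonged". The primary-analysis SAP (Section 3.9.1.5, Table 3-7) makes renal impairment an adverse event grouping of special interest. A creatinine rise is not the same thing as renal impairment, so this shows that the rule matters but says nothing about how often it would be used.

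**Working it through.** The conflict itself involves no arithmetic; the texts are set side by side.

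**1. Which table governs a renal event?** Tables 6-3 to 6-6 cover hematological, hepatic, QTcF and ILD/pneumonitis events. A renal event is in none of them, so it falls to Section 6.3.1.8 and hence to Table 6-7.

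**2. Comparison by grade at the first event.**

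| Event | Section 6.3.1.8.1 | Table 6-7 | Result |
|---|---|---|---|
| Grade 1 | no rule | no dose adjustment | no conflict |
| First grade 2 | discontinue | interrupt, restart at same dose | conflict |
| First grade 3 | discontinue | interrupt, restart one level lower | conflict |
| Grade 4 | discontinue | discontinue LEE011/placebo | agree |

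Table 6-7 also has entries for recurrence. They apply only after a restart that the renal sentence would already have ruled out, so they are not counted. Of the three entries reachable at grade 2 or higher, two conflict and one agrees.

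**3. Is precedence stated?** The mandatory clause in Section 6.3.1.4 names Tables 6-3 to 6-7 and Section 7.1.5.1, but not Section 6.3.1.8.1. Section 7.1.5.1 does not name renal impairment; it refers generally to Section 6.3, which contains both instructions. The chain leans towards stopping without saying that the renal sentence overrides the table.

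**4. What does *treatment* mean in the renal sentence?** Table 6-7 concerns LEE011/placebo only. Section 7.1.5.1 speaks of study treatment, which Section 6.1 defines as the triple combination. Section 6.1.4 lets endocrine therapy continue after LEE011/placebo stops. The renal sentence says only *treatment*, so its scope is open.

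**5. Which criterion sets the grade?** Adverse events are graded by CTCAE v4.03, but the protocol does not say which term or laboratory value defines renal impairment of grade 2. The SAP grouping collects events for analysis and gives a site no threshold.

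**6. How many patients could be affected?** The Amendment 7 summary reports 114 patients still on study treatment: 79 in the ribociclib arm and 35 in the placebo arm, 8 of whom had crossed over.

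- Assigned LEE011: 79 + 8 = 87.
- Placebo arm, not crossed over: 35 − 8 = 27.
- Ceiling if all of these cross over: 87 + 27 = 114.

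Placebo capsules no longer have to be given after Amendment 6, so a restart instruction matters only for LEE011. The figure of 87 is itself an upper limit, because Section 6.1.4 allows some patients counted as on study treatment to have stopped LEE011 already.

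**7. Is efficacy inference touched?** The primary-analysis SAP (Section 3.8.1.1) does not treat discontinuation of study treatment as a reason for censoring PFS. Protocol Section 10.7.2 makes analyses after Amendment 7 descriptive.

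**The case against.** The strongest reply is that the protocol already resolves the matter. A specific rule ordinarily prevails over a general one. The renal sentence sits inside Section 6.3.1.8, shortly after Table 6-7, and Section 6.3.3 treats Section 6.3.1 as a single body of dose-modification and stopping rules. Section 6.3.1.4 lets mandatory stops override the table's recommendations, and Section 7.1.5.1 brings in Section 6.3. On this view only a cross-reference is missing.

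Much of that stands. It is why discontinuation is taken here as the intended action and why the point is minor. A reader might infer that sites are obliged to restart; they are not, because Section 6.3.1.4 leaves room for clinical judgment and the restart entries are recommendations.

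The reply does not remove the problem. A site managing an on-treatment event has no reason to look under a heading about starting dose once Section 6.3.1.8 has sent it to the table. Amendment 7 edited Section 6.3.1.8 to name toxic epidermal necrolysis, for which the table's grade 4 entry already gives the right action, but did not name the renal event, for which it does not.

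**Conclusion.** The concern holds as a minor inconsistency in a safety instruction. Followed literally, Table 6-7 gives the wrong action for renal impairment at a first grade 2 and a first grade 3. This rests on taking Section 6.3.1.8.1 as the intended rule, which the documents favour but do not state.

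Three stronger readings are not supported:

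- The figures of 87 and 114 might be read as patients at risk of mismanagement. They are ceilings on exposure to LEE011. The documents give no rate of grade 2 or higher renal impairment, so no event count can be derived.
- A bias in PFS or OS might be inferred. The SAP's handling of discontinuation and the descriptive status of later analyses rule out an effect on the formal inference; what can change is patient management and drug exposure.
- A parallel conflict might be seen for unavoidable drugs with a known torsades risk, since Section 7.1.5.1 requires stopping for prohibited medication while Section 6.4.4 requires only interruption of LEE011/placebo. Section 6.4.3 frames the prohibition around combined treatment, and Section 6.4.4 is the specific rule for unavoidable use, so the exception is already implied. No change is proposed there.

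**What to change.** In Section 6.3.1.8 and in Table 6-7, add: *except renal impairment of grade 2 or higher: discontinue LEE011/placebo, see Section 6.3.1.8.1*.

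In Section 6.3.1.8.1, state two things:

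- that *treatment* means LEE011/placebo, with endocrine therapy handled under Section 6.1.4;
- which CTCAE v4.03 term or laboratory criterion defines the grade.

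If the sponsor intends the whole regimen to stop, the sentence should say that instead.

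The cost is a few lines in the next protocol amendment and a letter to sites. No new assessments are needed, and no sample size, power or alpha figure changes.

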#### 6.3.2 Follow-up for toxicities

Patients who complete treatment or whose treatment is interrupted or permanently discontinued due to an adverse event or abnormal laboratory value must be followed at least once a week for

4 weeks, and subsequently at 4-week intervals, until resolution or stabilization of the event. All patients will be followed up for safety up to 30 days following the last dose of study treatment (tamoxifen or a NSAI + goserelin + LEE011/placebo).

### **6.3.3 Anticipated risks and safety concerns of the study drug**

Appropriate eligibility criteria, as well as specific dose modification and stopping rules are included in this protocol. Refer to [Section 6.3.1](#) for details.

## **6.4 Concomitant medications**

### **6.4.1 Permitted concomitant therapy**

Medications required to treat AEs, manage cancer symptoms, concurrent diseases and supportive care agents, such as pain medications, anti-emetics and anti-diarrheals are allowed. Please consult the list of prohibited medications and the list of use with caution medications for further guidance.

The patient must be told to notify the investigational site about any new medications she takes after the start of the study treatment. All medications (other than study drugs) and significant non-drug therapies (including vitamins, herbal medicines, physical therapy and blood transfusions) administered within 30 days of study entry and during the study must be listed on the Concomitant medications/Significant non-drug therapies eCRF.

If patients take concomitant medications chronically, any change in dose or schedule of any concomitant medication throughout the study period should be clearly documented.

#### **6.4.1.1 Bisphosphonates and denosumab**

Bisphosphonates and denosumab are generally allowed with the following comments:

- Chronic concomitant bisphosphonate/denosumab therapy for the prevention of bone metastasis is not permitted.
- Bisphosphonate/denosumab therapy for the treatment of osteoporosis is permitted.
- Bisphosphonate/denosumab therapy for the prevention of skeletal related events for patients with bone metastases is permitted.
- If bisphosphonate/denosumab therapy is to be started after the first dose of study drug, prior consultation and approval by Novartis is required and the reason for its use must be clearly documented.

Patients taking concomitant medication chronically should be maintained at the same dose and dose schedule throughout the study period, as medically feasible. [REDACTED]

[REDACTED]

[REDACTED]

#### **6.4.1.2 Corticosteroids**

Chronic dosing of corticosteroids such as dexamethasone and prednisone is known to lead to induction of CYP3A enzymes, thereby potentially reducing LEE011 drug exposure to sub-therapeutic levels. Systemic corticosteroid treatment should not be given during the study, except for:

- Topical applications (e.g., for rash), inhaled sprays (e.g., for obstructive airways diseases), eye drops or local injections (e.g., intra-articular);
- A short duration (< 5 days) of systemic corticosteroids  $\leq$  to the anti-inflammatory potency of 4 mg dexamethasone (e.g. for chronic obstructive pulmonary disease, or as an antiemetic)

#### **6.4.1.3 Hematopoietic growth factors**

Prophylactic use of WBC growth factors with LEE011/placebo is not recommended.

#### **6.4.1.4 Palliative radiotherapy**

Palliative radiation is permitted. It should not be delivered to a target lesion. Cumulative courses of RT should not encompass >25% of irradiated bone marrow. (See [Appendix 4](#)).

If palliative radiotherapy is initiated after start of study treatment, the reason for its use must be clearly documented and progression as per RECIST 1.1 must be ruled out.

No dose modification of study treatment is mandated during palliative radiotherapy.

#### **6.4.1.5 Use of antiemetic medications**

LEE011 has low to minimal emetogenic potential according to the definition of antineoplastic agent emetogenicity ([Grunberg et al, 2010](#)). Antiemetic therapy can be used according to clinical guidelines for antineoplastic medications with low to minimal emetogenic potential for treatment and/or prevention of nausea and vomiting as a result of study treatment ([NCCN Clinical Practice Guidelines in Oncology. Antiemesis, 2016](#); [Roila F et al, 2016](#)).

Potential drug interaction between LEE011 and antiemetic medications should always be taken into consideration. An example of prohibited antiemetic medication is ondansetron that in combination with LEE011 may precipitate TdP. Refer to [Table 14-1](#) and [Table 14-2](#) of [Appendix 1](#) for a list of medications that are prohibited or allowed to be used with caution.

